8.2. Safety Assessments

Safety assessments will include the monitoring of AEs, physical examinations, and vital signs.

AEs will be reported and followed by the investigator as specified in Section 8.3 and Appendix 2.

Any clinically significant abnormalities will be followed by the investigator until clinical resolution (return to baseline) or until a clinically stable condition is reached, or until the participant has been deemed lost to follow-up after demonstration of due diligence of follow-up efforts.

The study will include the following evaluations of safety and reactogenicity according to the time points provided in the Schedule of Activities.

8.2.1. Physical Examinations

A physical examination, including height and body weight, will be carried out pre-vaccination on Day 1. At any other clinic visit, an abbreviated, symptom-directed examination may be performed if deemed necessary by the investigator based on any clinically relevant issues, clinically relevant symptoms, and medical history.

Physical examinations will be performed by the investigator or appropriately trained delegate. Any clinically relevant abnormalities or changes in severity noted during the review of body systems should be documented in the eCRF as an AE or SAE if it meets the criteria for an AE or SAE according to the protocol reporting requirements.

8.2.2. Vital Signs

Vital signs will be measured pre- and post-dose on Day 1. At non-vaccination visits, vital signs will be measured if deemed necessary by the investigator. Body temperature (oral route preferred), heart rate (beats per minute), respiratory rate (breaths per minute), and systolic and diastolic blood pressure (mmHg) will be assessed.

Blood pressure and heart rate measurements will be assessed, if possible, with a completely automated device. Manual techniques will be used only if an automated device is not available.

Sitting systolic and diastolic blood pressure and heart and respiratory rate measurements should be preceded by at least 5 minutes of rest in a quiet setting without distractions (eg, television, cell phones).

Confirmatory vital signs measurement can be performed if inconsistent with a prior measurement. Any abnormalities or changes in severity noted during the review of vital signs should be documented in the eCRF.

8.2.3. Pregnancy Testing

A urine pregnancy test for participants of childbearing potential will be performed at screening. Additional urine pregnancy tests may be performed, as determined necessary by the investigator or required by local regulation, to establish the absence of pregnancy at any time during the participation in the study.

8.3. AEs, SAEs, AESIs and Other Safety Reporting

Timely, accurate, and complete reporting and analysis of safety information, including AEs, SAEs, AESIs (including potential AESIs, refer to Section 8.3.6) and Product Quality Complaints (PQCs), from clinical studies are crucial for the protection of participants, investigators, and the sponsor, and are mandated by regulatory agencies worldwide. The sponsor has established standard operating procedures in conformity with regulatory requirements worldwide to ensure appropriate

reporting of safety information; all clinical studies conducted by the sponsor or its affiliates will be conducted in accordance with those procedures.

AEs will be reported by the participant (or, when appropriate, by a caregiver, surrogate, or the participant's legally acceptable representative) for the duration of the study.

Further details on AEs, SAEs, AESIs, and PQCs can be found in Appendix 2.

8.3.1. Time Period and Frequency for Collecting AE, SAE, and AESI Information

All AEs

AEs and special reporting situations, whether serious or non-serious, that are related to study procedures or that are related to non-investigational sponsor products will be reported from the time a signed and dated ICF is obtained until the end of the study/early withdrawal.

Clinically relevant medical events not meeting the above criteria and occurring between signing of ICF and moment of vaccination will be collected on the Medical History eCRF page as pre-existing conditions.

Solicited AEs, collected through a participant diary, will be recorded from the time of vaccination until 7 days post-vaccination.

All other unsolicited AEs and special reporting situations, whether serious or non-serious, will be reported from the time of vaccination until 28 days post-vaccination.

All SAEs and AEs leading to discontinuation from the study (regardless of the causal relationship) are to be reported from the moment of vaccination until completion of the participant's last study-related procedure, which may include contact for safety follow-up. The sponsor will evaluate any safety information that is spontaneously reported by an investigator beyond the time frame specified in the protocol.

See Section 7.2 for procedures associated with withdrawal of consent.

All AEs will be followed until resolution or until clinically stable.

SAEs

All SAEs occurring during the study must be reported to the appropriate sponsor contact person by study-site personnel immediately, but no later than 24 hours of their knowledge of the event.

Information regarding SAEs will be transmitted to the sponsor using the SAE Form and Safety Report Form of the eCRF, which must be completed and reviewed by a physician from the study site, and transmitted to the sponsor immediately, but no later than within 24 hours. The initial and follow-up reports of an SAE should be transmitted electronically or by facsimile (fax). Telephone reporting should be the exception and the reporter should be asked to complete the appropriate form(s) first.

AESIs

TTS is considered to be an AESI. Thrombotic events and/or thrombocytopenia (defined as platelet count below the lower limit of normal [LLN] range for the testing lab) are considered to be potential AESIs. All AESIs, including potential AESIs, will be reported to the sponsor from the moment of study vaccination until 6 months after the study vaccination (see Section 8.3.6).

8.3.2. Method of Detecting AEs, SAEs, and AESIs

Care will be taken not to introduce bias when detecting AEs, SAEs, or AESIs. Open-ended and nonleading verbal questioning of the participant is the preferred method to inquire about AE occurrence.

Solicited AEs

Solicited AEs are used to assess the reactogenicity of the study vaccine and are predefined local (injection site) and systemic events for which the participant is specifically questioned and which are noted by participants in their participant diary.

After vaccination, participants will remain under observation at the study site for at least 30 minutes for presence of any acute reactions and solicited events.

In addition, participants will record solicited signs and symptoms in a participant diary for 7 days post-vaccination. All participants will be provided with a participant diary and instructions on how to complete the participant diary (see Overview in Section 8). If a paper diary is used for this study, the study staff will transcribe the information provided by the participant into the relevant sections of the eCRF. If an e-diary is used, diary information will be transferred to the sponsor. After review and verbal discussion of the initial diary entries with the participant, the investigator will complete their own assessment in the relevant sections of the eCRF. Once a solicited sign or symptom from a participant diary is considered to be of severity Grade 1 or above, it will be recorded as a solicited AE.

Solicited Local (Injection Site) AEs

Participants will be asked to note in the participant diary occurrences of injection site pain/tenderness, erythema and swelling at the study vaccine injection site daily for 7 days post-vaccination (day of vaccination and the subsequent 7 days). The extent (largest diameter) of any erythema and swelling should be measured (using the ruler supplied) and recorded daily. The case definitions for solicited injection site events can be found in the references (Gidudu 2012; Kohl 2007).

Solicited Systemic AEs

Participants will be instructed on how to record daily temperature using a thermometer provided for home use. Participants should record the temperature (oral route preferred) in the participant diary in the evening of the day of vaccination, and then daily for the next 7 days approximately at the same time each day. If more than 1 measurement is made on any given day, the highest temperature of that day will be used in the eCRF.

Fever is defined as endogenous elevation of body temperature $\ge 38.0^{\circ}\text{C}$ ($\ge 100.4^{\circ}\text{F}$), as recorded in at least 1 measurement (Marcy 2004).

Participants will also be instructed on how to note signs and symptoms in the participant diary on a daily basis for 7 days post-vaccination (day of vaccination and the subsequent 7 days), for the following events: fatigue, headache, nausea, and myalgia.

Unsolicited AEs

Unsolicited AEs are all AEs for which the participant is not specifically questioned in the participant diary.

For details regarding AESIs, refer to Section 8.3.6.

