2.3.1. Risks Related to Study Participation

The following potential risks for the Ad26/protein preF RSV vaccine will be monitored during the study:

Risks Related to Ad26/protein preF RSV Vaccine

The Ad26/protein preF RSV vaccine is being studied in 4 ongoing studies in more than 6500 participants aged 60 years and above, including participants with comorbidities, to assess safety and immunogenicity, and to investigate whether the vaccine prevents RSV disease. In these studies, the most commonly reported solicited local AEs were injection site pain/tenderness and swelling (mild to moderate). The most frequently reported solicited systemic AEs were fatigue, muscle pain, headache, chills, joint pain and nausea, which were mild to moderate in severity. These solicited AEs were short-lived and resolved within a few days. Overall, available results from these studies show the vaccine to be well-tolerated with no safety concerns.

General Risks Related to Vaccination

In general, IM injection may cause local itching, warmth, pain, tenderness, erythema/redness, induration, swelling, arm discomfort, or bruising of the skin. Participants may exhibit general signs and symptoms associated with IM injection of a vaccine and/or placebo, including fever, chills, rash, myalgia, nausea/vomiting, headache, dizziness, arthralgia, general itching, and fatigue. These side effects will be monitored, but are generally short-term and do not require treatment.

Syncope can occur in association with administration of injectable vaccines. Syncope can be accompanied by falls. Procedures should be in place to avoid falling injury. If syncope develops, participants should be observed until the symptoms resolve. Fear of injection might lead to fainting and fast breathing.

Participants may have an allergic reaction to the vaccination. An allergic reaction may cause a rash, urticaria, or even anaphylaxis. Severe reactions are rare. Participants with a known or suspected allergy, or history of anaphylaxis or other serious adverse reactions to vaccines or their excipients (including specifically the excipients of the study vaccine) will be excluded from the study.

After vaccination, participants will remain at the study site for at least 30 minutes and will be closely observed by study staff. Necessary emergency equipment and medications must be available in the clinic to treat severe allergic reactions.

Pregnancy and Birth Control

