3. OBJECTIVES AND ENDPOINTS

	Objectives	Endpoints			
Pri	Primary				
•	To assess the safety and reactogenicity of Ad26.RSV.preF-based RSV vaccine in healthy adults aged 18 to 59 years	 Solicited local (injection site) and systemic AEs for 7 days after vaccination Unsolicited AEs for 28 days after vaccination Serious adverse events (SAEs) and adverse events of special interest (AESIs) until 6 months after vaccination 			
•	To assess the safety and reactogenicity of Ad26.RSV.preF-based RSV vaccine in adults aged 18 to 59 years at high-risk of severe RSV disease	 Solicited local (injection site) and systemic AEs for 7 days after vaccination Unsolicited AEs for 28 days after vaccination SAEs and AESIs until 6 months after vaccination 			

Objectives	Endpoints
• If non-inferiority is demonstrated in adults: To demonstrate the non-inferiority of the humoral response to the administration of Ad26.RSV.preF-based vaccine in high-risk adults aged 18 to 59 years versus in adults aged 65 years and older	 Neutralizing antibody titers against RSV A2 strain at 14 days after vaccination Seroresponse rate* at 14 days after vaccination as determined by neutralization assay (VNA-A2).

^{*} Seroresponse is defined as a 4 fold increase from baseline in Day 15 antibody titers.

Sec	Secondary				
•	Investigate the vaccine-induced immune responses post-vaccination	Pre-F ELISA antibody titers at 14 days after vaccination			
Exp	Exploratory				
•	To assess the persistence of immune response post-vaccination	 Pre-F ELISA antibody titers at 6 months after vaccination Neutralizing antibody titers against RSV A2 strain at 6 months after vaccination 			
•	To further explore the humoral immune responses elicited by the Ad26.RSV.preF-based vaccine	 Neutralizing antibody titers against RSV B strains and other RSV A strains Neutralizing antibody titers against Ad26 Molecular and functional antibody characterization including antibody avidity, Fc-mediated effector function, subtyping and isotyping, glycosylation patterns, antibody sequencing for repertoire[†] 			

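### The diary omits chills and joint pain, two of the six commonest solicited systemic reactions in the vaccine's earlier studies, so both are likely under-ascertained and cannot appear in the 7-day solicited tables

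*Protocol*

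**What the plan says.** Safety and reactogenicity in healthy and in high-risk adults aged 18 to 59 are primary objectives (Protocol section 3). The first endpoint under each is "Solicited local (injection site) and systemic AEs for 7 days after vaccination". Unsolicited events to 28 days are a second endpoint under the same objectives.

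Protocol section 8.3.2 states the role of the diary: "Solicited AEs are used to assess the reactogenicity of the study vaccine". For systemic events it asks for a temperature, "Participants should record the temperature (oral route preferred) in the participant diary", and for daily symptom entries "for the following events: fatigue, headache, nausea, and myalgia". Everything else falls under the residual definition: "Unsolicited AEs are all AEs for which the participant is not specifically questioned in the participant diary".

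Protocol section 2.3.1 summarises earlier experience: "The Ad26/protein preF RSV vaccine is being studied in 4 ongoing studies in more than 6500 participants aged 60 years and above". For those studies it reports: "The most frequently reported solicited systemic AEs were fatigue, muscle pain, headache, chills, joint pain and nausea". A separate paragraph on injections in general lists chills and arthralgia with many other symptoms and adds: "These side effects will be monitored, but are generally short-term and do not require treatment".

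The toxicity scales in Appendices 6 and 7 have rows for vomiting and diarrhea, which the diary does not ask about, but none for chills or joint pain. SAP section 5.4.1.2 tabulates solicited and unsolicited events separately. It plans time-to-onset and duration tables for the solicited events only. SAP section 5.4.1.4 counts a participant who reports no event as having had none.

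**The concern.** The sponsor's own summary describes chills and joint pain as solicited events in the earlier studies and ranks them among the commonest. This trial keeps the other four symptoms on that list and drops these two without explanation. A daily prompt for a named symptom usually finds more mild, short-lived cases than a general question about how the participant has been.

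What is at stake is the description of reactogenicity in the two populations for which it is a primary objective. A reader of the 7-day solicited tables will find no line for either symptom and may take that to mean they were rare. A reader who sets those tables beside the earlier studies will be comparing different symptom lists.

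**Working it through.** **Step 1. The plan's own safety figures.** Protocol section 9.2.2 gives the probability of seeing at least one event, 1 − (1 − p)^n. With n = 315 and p = 0.5%, 1% and 2.5% this gives 79.4%, 95.8% and 99.97%. With n = 630 it gives 95.7%, 99.8% and 100%. The upper limit after zero events, 1 − 0.05^(1/n), is 0.95% for 315 and 0.47% for 630. All agree with the protocol. They concern rare events and say nothing about how completely a frequent symptom is collected, so they neither support nor weaken this point.

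**Step 2. The lists side by side.**

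| Event | Commonest solicited events in earlier studies, aged 60 and above (Protocol 2.3.1) | Asked for in this diary (Protocol 8.3.2) | Grading row (Appendices 6 and 7) |
|---|---|---|---|
| Fatigue | yes | yes | yes |
| Muscle pain | yes | yes | yes |
| Headache | yes | yes | yes |
| Nausea | yes | yes | yes |
| Chills | yes | no | no |
| Joint pain | yes | no | no |
| Fever | not named | yes, by temperature | yes |

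Four of the six named events are solicited and two are not.

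**Step 3. The route for the two omitted events.** Under section 8.3.2 they are unsolicited. They reach the database if the participant mentions them at a safety contact or when the diary is reviewed. They then appear by preferred term in the unsolicited tables to Day 28. They cannot enter any solicited table.

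**Step 4. Under-ascertainment of each symptom (assumed values).** Recorded rate = true rate × fraction captured. The documents give neither input. A true rate of 10% to 40% and a capture of 25% to 100% give recorded rates from 10% × 25% = 2.5% to 40% × 100% = 40%. For example, a true rate of 20% is 63 of 315 participants in one active group. At 50% capture, 31.5 would be expected in the data, a recorded rate of 10%.

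**Step 5. Effect on the proportion with any solicited systemic event (assumed values).** This proportion loses only participants who have chills or joint pain and none of fever, fatigue, headache, nausea or myalgia. Let p be the proportion with chills or joint pain, and o the share of those who also have a solicited symptom. Shortfall = p × (1 − o).

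| p | o = 100% | o = 90% | o = 75% | o = 50% |
|---|---|---|---|---|
| 10% | 0 | 1 point | 2.5 points | 5 points |
| 20% | 0 | 2 points | 5 points | 10 points |
| 30% | 0 | 3 points | 7.5 points | 15 points |

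The loss in Step 4 is not the shortfall in Step 5. A symptom can be badly under-recorded while the composite does not move.

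**Step 6. What a combined table could recover.** If a fraction c of the otherwise missed participants report the symptom unprompted, the table recovers p × (1 − o) × c. With p = 20%, o = 75% and c = 50%, that is 2.5 of the 5 points. The table discloses the gap and narrows it, but does not close it.

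**The case against.** The strongest reply is that nothing reported is lost. Section 8.3.2 prefers open-ended questions about adverse events. There are safety contacts at Days 8, 15 and 29, and the diary is discussed with the participant. Reported chills and arthralgia are graded under the general guidance in Protocol section 10.2.3. They are also tabulated within an endpoint that belongs to the same primary objective. This stands, and it rules out saying that participants are never asked. They are asked, but not by symptom name.

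The list in section 2.3.1 comes from people aged 60 and above, so the frequency at ages 18 to 59 is not documented. This also stands. It limits any claim about size, but it gives no reason to leave the two symptoms out when the younger groups are the ones being characterised.

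The sentence promising monitoring might look like a contradiction of the diary list. It is not. Its paragraph covers injections in general and also names rash, dizziness and general itching, none of which is solicited. Collecting unsolicited events is a form of monitoring.

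Lastly, safety is analysed descriptively (Protocol section 9.4.4), so no test, power or success criterion is affected. That is correct.

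The reply leaves three things unanswered: the missing rationale, the weaker ascertainment, and the absence of both symptoms from the tables that the protocol itself designates for assessing reactogenicity.

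**Conclusion.** The omission is confirmed and unexplained. Chills and joint pain are likely to be under-ascertained, cannot appear in the 7-day solicited results, and make those results not like-for-like with studies that solicited them. That ascertainment will be lower is a judgement about prompted against unprompted reporting, not a figure in the documents.

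A reader might infer that the primary reactogenicity endpoint is therefore understated. The documents do not support this as a fact. The effect on the composite is zero if every affected participant also has a solicited symptom, and neither the rates nor the overlap are given. The range of 0 to 15 points rests wholly on the values assumed in Step 5.

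A reader might also infer that Grade 3 or higher rates are biased low. That is not supported either: section 2.3.1 describes the frequent systemic events as mild to moderate and short-lived.

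This is a worthwhile, inexpensive improvement to the reporting of a primary safety objective. It does not threaten the trial's conclusions on immunogenicity.

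**What to change.** In SAP section 5.4.1.2, with the layout in the data presentation specifications, add one reactogenicity table by cohort and group:

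- Show unsolicited chills and arthralgia with onset on the day of vaccination or in the following 7 days, beside the solicited systemic events.
- Label each row by collection mode, solicited or unsolicited.
- Give the proportion with any systemic reaction both with and without these two events.
- State the denominator for each row, because SAP section 5.4 uses different denominators for solicited and unsolicited events. State also how partial onset dates are treated.

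This needs no new data and costs one table.

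For any participants still to be vaccinated, add both symptoms to the diary and to the solicited-event eCRF page, with severity wording, since Appendices 6 and 7 have none. The Amendment 2 summary reports Cohort 1 enrollment as completed in the other countries, and Spain enrolls only Cohorts 2 and 3. A diary change therefore cannot help Cohort 1. It would also create two collection modes, between cohorts and within any cohort still enrolling, and these must be reported separately.

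If the diary is left as it is, the protocol should give the reason for the shorter list, and the study report should say that the solicited results are not directly comparable with those of studies that asked about chills and joint pain.

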8.3.3. Follow-up of AEs, SAEs, and AESIs

The investigator is obligated to perform or arrange for the conduct of supplemental measurements and evaluations as medically indicated to elucidate the nature and causality of the AE, SAE, AESI, or PQC as fully as possible. This may include additional laboratory tests or investigations, histopathological examinations, or consultation with other health care professionals.

AEs and the special reporting situation of pregnancy will be followed by the investigator as specified in Appendix 2.

8.3.4. Regulatory Reporting Requirements for SAEs

The sponsor assumes responsibility for appropriate reporting of AEs to the regulatory authorities. The sponsor will also report to the investigator (and the head of the investigational institute where required) all suspected unexpected serious adverse reactions (SUSARs). The investigator (or sponsor where required) must report SUSARs to the appropriate IEC/IRB that approved the protocol unless otherwise required and documented by the IEC/IRB. A SUSAR will be reported to regulatory authorities unblinded. Participating investigators and IEC/IRB will receive a blinded SUSAR summary, unless otherwise specified.

